The project will create perspectives about the extent of the problem, which patients are at particular risk, as well as the future disease burden and thus the future need for resources.

The project will generate ideas to improve treatment in the future and thus has the potential to improve the quality of life for patients in the future.

Publication

The project's results are planned to be published as a series of articles in peer-reviewed and international journals.

Economy and budget

The project is supported by Rigshospitalets Research Fund and "Danmarks" fund: "sundhedsdonationer".

Background

About knee arthroplasty and revisions.

Knee replacement or arthroplasty of the knee joint is performed in large numbers all over the world (1). The number of procedures performed has increased greatly in the last 30 years, both in Denmark and internationally (2). The first operation with the insertion of an endoprosthesis in the knee joint is called a primary knee replacement, and the term is used for the operation and the prosthesis. Primary knee arthroplasty is generally a safe operation that results in a significant improvement in the quality of life in the vast majority of patients, and more than 90% are satisfied with the result one year after surgery in Denmark (3).

In Denmark, over the past 20 years, more than 150,000 first-time knee replacement surgeries have been performed, and in 2020 alone, the number was approx. 10,500 operations (3). Many studies have been conducted in recent years with a focus on prevention and conservative treatment (1) of knee osteoarthritis. However, the need for operative intervention is increasing (2). The reason is presumably an increase in the proportion of elderly people in the population and greater expectations for a physically active old age without disease-related limitations. Furthermore, it is expected that the BMI of the population will increase, and that this will also increase the need for knee replacements (1).

As with all operative interventions, complications can occur after primary knee arthroplasty. Some of these complications lead to revision, which is defined as a reoperation in which a component of a knee prosthesis is inserted, removed or replaced.

Size of the problem

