knee or how many patients live with a n-grade revision in Denmark. The lifetime risk for multiply revisions is not known either.

Indications for revision and re-revision

There are several indications for revision of a knee replacement, such as aseptic loosening and infection (1). However, there is no consensus in the literature as to which cause is the most frequent, as aseptic loosening and infection are alternately stated as the most frequent cause(4, 10, 12, 14, 15). Discussion exists concerning whether infection will become the most frequent cause in the future(5, 12). Other causes are persistent pain, instability, periprosthetic fracture, metallosis and stiffness (1, 3).

Aseptic loosening is defined as the mechanical loosening of the prosthesis from the bone, and without ongoing infection around the prosthesis. Aseptic loosening typically occurs due to wear and tear of the prosthetic material or the polyethylene liner(1, 12, 14).

Infection around the prosthesis is the most feared complication, as bacteria form biofilms around the prosthetic material and break down the surrounding tissue prosthesis. Infection is very difficult to remove due to biofilm, and it often leads to structural complications as the infection weakens the tissue that will receive a new prosthesis(1). Typically, a deep infection is treated with either one-stage or two-stage revision, but prosthesis survival is generally low (16). Infection is believed to be the biggest cause of multiple revisions, precisely because of the low prosthesis survival compared to aseptic solution(10, 14, 17).

Risk factors for revision and re-revision

Several risk factors for revision after primary knee arthroplasty have been described. These are age, sex, BMI, previous surgery on the same knee, type of implant inserted and method of implantation, patient psychological factors and surgeon-related factors (1).

Older age is generally associated with lower risk of revision, and younger age is associated with higher risk of revision(1, 15, 18-22). Male sex, BMI >35 and previous procedures performed on the same knee have also been shown to be risk factors for revision(1, 12, 15, 23). The choice of inserted implant has also been shown to have an effect on the cumulative

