Landspatientregisteret (LPR) is a national and clinical database administered by the Danish Health Authority since 1976. All information generated when a patient is treated by the public health service is reported here. In addition to information regarding procedures and admissions, the register contains information on residence, partner status, level of education, income, comorbidities and emigration amongst others. Operations are recorded according to the NOMESCO classification, while diagnoses are coded according to the ICD-10 classification.

Identification of primary procedures

We will determine the cohort of primary procedures from DKR (called P-DKR) by identifying all primary procedures performed from January 1st 1998 to December 31st 2021. P-DKR is then transferred to Danmarks Statistik (DS). Through DS, all primary procedures in the observation period will be identified using NOMESCO operation codes (KNGB*) and these will be collected in a cohort called P-SD. P-DKR and P-SD will be joined into a cohort called PRIM and this cohort will best describe all primary procedures performed in Denmark during the observation period.

Identification of revision procedures

The DKR cohort of revisions (R-DKR) will be identified by all registrations marked as revisions during the observation period. R-DKR is also transferred to DS. All revisions will be identified in DS as R-DS using the NOMESCO operation codes KNG* (knee procedure), KNGC* (revision of knee), KNGG* (arthrodesis) and KNFQ19 (femur amputation). The cohorts R-DKR and R-DS will be combined and called REV. This cohort will best describe revision procedures performed in Denmark during the observation period.

Insertion of cement spacers presents a special registration problem, as different registration practices exist. Some use KNGS codes (eg KNGC59A – Insertion of spacer in a knee joint in connection with revision). We intend to not consider spacer insertion as a revision. For example a two-stage revision will be considered as one revision.

Organization of data

A table (G) with PRIM and REV will be created. G will contain information on revisions, deaths, disappearances, emigration and the associated dates. For each knee joint in PRIM and for each date in the observation period, it will be possible to describe the status of the knee joint.

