#### **Data management, for both registers.**

Definition of a revision: A revision is defined as the exchange, addition, or removal of a knee prosthesis component (1). However, knee arthrodesis and amputation are not included in this study.

Definition of major revision: A major revision is defined as exchange of the femoral component and/or the tibial component with subgroups of tibial, femoral and all component exchange (2).

Definition of minor revision: A minor revision is defined as the exchange of polyethylene liner and/or addition or revision of the patella component. Insertion/removal/exchange of spacers are also included in this category (2).

Population: The population is defined as the number of alive citizens in the state of Denmark. Annual populations are defined as the population in Denmark on the 1st of January that year. Additional data for sex and age of the population is acquired. Data for the population is acquired from Danmarks Statistik (3).

In case of disagreement between registers: In cases of discrepancy between the two registers, Landspatientregisteret will overrule the Danish Knee arthroplasty register concerning following variables:

- Laterality
- Date of surgery
- Gender
- Age
- Performing institution

In cases of discrepancy between the two registers, the Danish Knee arthroplasty register will overrule Landspatientregisteret concerning following variables:

- Procedure code
- Revision of tibia
- Revision of femur
- Indication

Calculation of standardized prevalence: Annual standardized prevalence is calculated as the number of patients living with a n-grade revision during a given year as a proportion of the population in Denmark (the 1st of January that year) (3). The prevalence is then multiplied by 100,000 for standardization. This is done for each level of revision, each year. E.g., the standardized prevalence for 1998 is calculated as:

$$\text{Standardized prevalence, 1998} = \frac{\text{Number of knees living in 1998 with a } n - \text{ grade revision}}{\text{Total population in Denmark in 1998}} * 100,000$$

The prevalence is only calculated for revisions performed between January 1st 1998 and December 31st 2021.

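### The protocol's spacer rule does not say which stage of a two-stage revision counts; read literally, a prosthesis removed for a spacer and never re-implanted scores zero revisions, against the protocol's own definition and the SAP's opposite rule

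*Protocol*

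**What the plan says.** The protocol's Background (About knee arthroplasty and revisions) has a revision "defined as a reoperation in which a component of a knee prosthesis is inserted, removed or replaced". Removal alone therefore qualifies.

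Under Material and methods, Identification of revision procedures, spacers are singled out: "Insertion of cement spacers presents a special registration problem, as different registration practices exist". The rule adopted is "We intend to not consider spacer insertion as a revision", followed by its intended effect: "For example a two-stage revision will be considered as one revision". The same section builds the combined revision cohort (REV) from two sources. One is the Danish Knee Arthroplasty Register (DKR), whose revision cohort "will be identified by all registrations marked as revisions during the observation period". The other is a set of national-register codes that includes KNGG* for arthrodesis and KNFQ19 for femoral amputation. Table G then holds the status of every knee on every date.

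SAP section 3 also makes removal a revision: "A revision is defined as the exchange, addition, or removal of a knee prosthesis component". It leaves arthrodesis and amputation out of the study and classes insertion, removal and exchange of spacers as minor revisions. KNGC59A (spacer) is in its minor-revision list, and DKR implant codes 10 and 11 (cement spacers) are among its revision types. SAP section 4 lists no deviations from the protocol. The SAP covers incidence and prevalence only, so WP-A2 and WP-A3 rest on the protocol's rule.

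**The concern.** The rule is meant to stop a two-stage revision from counting twice. It does so by dropping the spacer operation, which leaves re-implantation as the natural event to count. That works when stage two takes place. When it does not, the operation that took the prosthesis out may be the only one on record, and it is the one that is dropped. In completed cases the same reading dates the failure at re-implantation, although the prosthesis left the knee at stage one.

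The loss would be selective. The protocol links two-stage revision to deep infection and states "Infection is believed to be the biggest cause of multiple revisions". Indication, with infection named first, is one of the WP-A2 factors. Under the WPA2 formula (n-grade revisions divided by knees with n-1 revisions) an affected knee is in the denominator and missing from the numerator. The lifetime risks in WP-A3 start from the same data.

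**Working it through.** The plan has no figure on this point to reproduce. The check is to count revisions under each rule for three knee histories, then to bound the scale.

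**Counts.** History A is a completed two-stage revision. History B is removal with a spacer and no re-implantation. History C is removal with a spacer, then arthrodesis or amputation (salvage).

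| Rule | A | B | C |
|---|---|---|---|
| Protocol definition alone, salvage counted | 2 | 1 | 2 |
| Literal spacer rule, salvage counted through REV | 1 | 0 | 1 |
| Literal spacer rule, salvage kept as a separate event | 1 | 0 | 0 |
| Episode rule, salvage counted | 1 | 1 | 2 |
| Episode rule, salvage separate | 1 | 1 | 1 |
| SAP, all revisions | 2 | 1 | 1 |
| SAP, major revisions, stage one coded only KNGC59A | 1 | 0 | 0 |

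The definition alone gives 2 for A, against the protocol's wish for one. The literal spacer rule gives 0 for B, against the definition. Only a rule that links the stages gives 1 for both A and B, and the protocol has no such rule. The SAP's all-revisions analysis counts A twice. Its major-revision analysis can count B as zero.

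**Effect on the WPA2 ratio.** If a share f of n-grade revisions is lost, the numerator is multiplied by (1 - f) and the denominator is unchanged, so the relative downward bias is f. At grade n+1 the lost knee is also missing from the denominator, so the direction there is less certain.

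**Scale.** The one documented input is 1,048 revisions in 2020 (protocol Background, Size of the problem). All the shares below are assumptions.

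- Route 1: f = (share of revisions that are spacer first stages) x (share never re-implanted), each 5% to 20%. Low: 0.05 x 0.05 = 0.25%, and 1,048 x 0.0025 = 2.6 knees a year. High: 0.20 x 0.20 = 4%, and 1,048 x 0.04 = 41.9.
- Route 2: f = (infection share, 20-30%) x (two-stage share of those, 30-60%) x (never re-implanted, 5-20%). Low: 0.20 x 0.30 x 0.05 = 0.3%, or 3.1 knees a year. High: 0.30 x 0.60 x 0.20 = 3.6%, or 37.7.
- Within infection revisions under Route 2: 0.30 x 0.05 = 1.5% to 0.60 x 0.20 = 12%.

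As an illustration, take the protocol's 20-year first-revision figure of 13% as complete. A loss of 0.3% gives 13 x 0.997 = 12.96%, and a loss of 4% gives 13 x 0.96 = 12.48%.

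**The case against.** The strongest reply is that the protocol never names re-implantation as the counted event. The rule excludes spacer insertion, not removal of the prosthesis, and counting an episode once from its removal also fits the wish for one revision. This stands in part: the protocol is silent on the counted stage and its date. But counting from removal means ignoring the later re-implantation, and nothing in the text says to do that.

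A second reply is that other routes capture the event. A removal marked as a revision in DKR enters the cohort, and the protocol prefers DKR where the sources disagree. This also stands, and it makes the figures above upper bounds. It depends, however, on the registration practice that the protocol itself calls variable. The national-register revision codes listed in the SAP offer little help: they are secondary insertions, the spacer code and one code for placement of medication, and none names removal of a prosthesis.

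A reader might infer that knees ending in arthrodesis or amputation are lost as well. The documents do not support that as a general statement: both code groups enter REV, so such a knee scores zero only if salvage is handled as a separate event. If salvage is counted, what the literal rule loses is the removal that came before it. A reader might also infer that later revisions on affected knees are misgraded. That largely does not follow, because the affected knees are those never re-implanted.

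Finally, the SAP's all-revisions analysis counts a retained-spacer knee at least once. That is correct, but it reverses the protocol's rule without saying so. In the major-revision analysis, a stage-one record with the DKR femoral or tibial flag set would count, while one coded only as a spacer would not.

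**Conclusion.** The point holds in a limited form. As written, the protocol's spacer rule gives zero revisions to a knee whose prosthesis was removed for a spacer and never replaced, when stage one is recorded only as a spacer insertion. That contradicts the protocol's definition. The documents do not establish that the protocol counts only re-implantations, nor that every uncompleted two-stage revision is lost.

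The bias in the n-grade cumulative revision rate and in the lifetime risk is downward and falls mainly on infection. Its size cannot be known from the documents: roughly 0.3% to 4% of revisions under assumed shares, and less where DKR captures the removal. On the overall rates this is small; within the infection indication it could reach 12% at the top of the assumed range. The conflict between protocol and SAP on spacers needs no assumption: the two rules are opposite and no deviation is declared. This should be corrected before the WP-A2 and WP-A3 analyses.

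**What to change.** Replace the spacer sentence in the protocol with one episode rule, for example:

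> Removal of the prosthesis with spacer insertion counts as one revision, dated at that operation. Later spacer exchanges and the first re-implantation on the same knee belong to the same episode and add no grade. An episode without re-implantation still counts as one revision.

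A completed two-stage revision then still counts once, as intended, and uncompleted ones are kept. Three further changes are needed:

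- Use the episode date for event times in WP-A2 and WP-A3.
- State whether arthrodesis and amputation in REV add a revision grade or are a separate event.
- Align the SAP's spacer rule with the protocol, or enter the difference in SAP section 4. Also say how an episode is placed in the major and all-revisions analyses.

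The cost is a few sentences and some code. The spacer codes are already listed in the SAP (KNGC59A; DKR codes 10 and 11). The downside is record linkage: each spacer record must be tied to the next re-implantation on the same knee, with some misclassification where spacers are poorly coded.

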Since 1998, the Danish Knee Arthroplasty Register has registered knee replacements (both primary and revisions) performed in Denmark. Traditionally, the most important measure within register research of knee replacements has been the cumulative revision rate, which describes how many patients experience a revision after a given period of time. Around 13% of primary knee arthroplasties are revised for the first time within the first 20 years in Denmark. In the last 20 years, more than 20,000 revisions have been performed. In 2020, 1048 were performed (3).

As the number of performed annual primary procedures increases, so will the number of annual revisions. Upfill-Brown et al. examined the number of revisions in the United States in the period 2012 to 2019. The number of revisions increased by 29.6% per year (4). See **Figure 1**. Kurtz et al. and Pavel et al. have projected, on the basis of large national registries in the USA and England, containing several hundreds of thousands of patients, that the annual number of revisions after primary knee arthroplasty will increase over 300% in England and over 600% in the USA in 2030 compared to the number of revisions in 2005 (2, 5). See **Figure 2**.

Figure 1: Projection of the annual incidence of performed revisions in the United States.

From Uffill-Brown et al.

[figure not shown]
[figure not shown]

Fig. 2

The projected number of revision total hip arthroplasty (THA) and total knee arthroplasty (TKA) procedures in the United States from 2005 to 2030.

Figure 2: Projection of the annual incidence of revisions carried out in England and Wales.

From Patel et al.

Graph showing the projected total number of revision knee arthroplasties in England and Wales between 2013 and 2030.

[figure not shown]
Re-revision

Unfortunately, even after revision, there is a risk of new complications, which may necessitate another revision (re-revision). In some patients, one complication follows another, and these patients may require several revisions. We use the term *multiply revised* when a patient experience at least three revisions of their knee replacement. In principle, there is no upper limit to the number of revisions in a knee, and some knees are revised more than 10 times. Some patients may end with an arthrodesis or amputation (6, 7).

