There is a paucity of studies investigating multiple revised patients. Deere et al. investigated the subject in 2019, containing just over 30,000 patients from the English register NJR(8). The study found that 20% of those revised for the first time were revised a second time after 13 years. 20% of those were revised for the third time after 5 years, and 20% of those were revised again for the fourth time within 3 years. The risk of multiply revisions was higher in men and in younger patients. Also, the study found that the risk of revision increased as time between revisions decreased.

In 2010, Ong et al. investigated the risk of revision after primary and first revision after total knee arthroplasty (TKA) and total hip arthroplasty (9). The study contained data from 73,000 primary knee arthroplasties, and 1600 revisions performed between 1997 and 2006. The study found that the risk of a second revision was 6 times higher than the risk of a first revision. See **Figure 3**:

Figure 3: Graph illustrating risk of revision after primary and first revision. From Ong et al.

In 2021, Belt et al. investigated the association of the indication for revision and the risk of re-revision (10). The study found that the cumulative re-revision rate was 19% after 8 years (significantly higher than the cumulative revision rate after primary knee arthroplasty). Klasan et al. found that the re-revision rate after revision due to aseptic loosening was 12% over a 16-year period (1999-2015) in New Zealand (11). In 2018, Postler et al. examined a smaller population of 300 patients in a prospective, single-centre study (12). The study found that re-revisions were performed 4 years since the last revision, while first revisions were performed after 8 years since primary knee arthroplasty.

A Danish study was performed in 2022, by Arndt et al. which investigated rate of re-revision after revision for either “aseptic resolution” or “pain without resolution” (13). The study included data from 4299 revisions from 1997 to 2018 from the Danish Knee Arthroplasty Register. The study found a cumulative revision rate of 23% after 20 years for patients with pain without loosening. For patients with aseptic loosening, the cumulative revision rate after 20 years was 19%.

No study has investigated the cumulative revision rates stratified by number of previous revisions in a national population. It is not known how many patients live with a revision

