Revision after knee arthroplasty is associated with significant financial costs for both the patient and society. For the patient, this is associated with a loss of ability to work, as described in the previous section. For Denmark's public health service, revision surgery is a significant financial burden. Revision surgery is more complex, requires longer operating time, more experienced surgeons, more advanced equipment and prostheses, and is usually performed in patients with comorbidities and who require more medication and a longer hospital stay (6, 45, 46). In addition, revision due to infection is more than 3 times as expensive as revision surgery for other reasons, which is a cause for concern as studies have found an increasing incidence rate of revisions due to infection (5, 12, 45-47). Gabor et al. conducted a prospective study in 2019 which suggested that centralizing revision surgery has the potential to limit costs (48).

Purpose

There is a need to prevent the complications that lead to repeated revisions, and there is a need to improve revision outcomes. Many unanswered questions are presented in the background section. Answers to these are needed in order to 1) predict the future need for

resources, 2) monitor the effects of changes in treatments and organization, and 3) give patients realistic expectations about the future when they undergo knee replacement surgery.

This research project aims to obtain new knowledge about the epidemiology of revisions after knee arthroplasty and to answer the following questions:

1. How many patients live with a multiple revision knee (i.e. prevalence) and how many multiple revisions procedures are performed (i.e. incidence)?
2. Are some demographic groups particularly at risk?
3. What is the risk of needing a revision after n-grade revision?
4. What future demands can be expected of surgeons and hospitals to provide care for patients needing revisions?
5. What is the lifetime risk of multiple revisions?

In order to answer the research questions, the research project is divided into 3 work packages.

WP-A1: Incidence and prevalence

The purpose of this work package (WP) is to determine the evolution of the incidence and prevalence of revisions of various degrees over the last two decades. We also aim to develop a mathematical model that predicts future incidence and prevalence based on demographic data as well as historical information of primary knee arthroplasty.

Research questions

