- 1) What is the annual incidence of revisions of various degrees, and how has the incidence changed during the last 20 years?
- 2) What is the current prevalence of n-grade revisions, and how has the prevalence changed during the last 20 years?
- 3) What is the relationship between the annual incidence of revisions of n-grade with the incidence of primary procedures in the preceding years?

WP-A2: Cumulative Revision Rates (CRR)

The purpose of this WP is to determine the cumulative revision rate (CRR) for revisions of different grades (number of previous revisions) to generate information that can be used for informing patients preoperatively.

Research questions:

1. What is the CRR for n-grade revision?
2. Is CRR influenced by demographic and surgical variables such as sex, age, education, implant type, place of residence, income, operative technical conditions and the indication of revision such as infection, aseptic loosening, instability, pain without reason?

WP-A3: Lifetime risk of multiple revisions

The purpose of this WP is to determine the lifetime risk of revision of various grades as well as the lifetime risk of arthrodesis and amputation. These risks will be investigated in relation to demographic and surgical variables.

Research questions:

1. What is the lifetime risk that a patient with a given combination of demographic and surgical variables will need n-number of revisions after primary arthroplasty?
2. As above but with arthrodesis and amputation as the risk event.

Review of literature

To gather relevant background information for this protocol, MEDLINE via pubmed was searched to find relevant literature in the field. The MESH words "knee replacement" and "reoperation" were used. We wanted to identify articles that either described epidemiological findings regarding multiple revision knee arthroplasties or described risk factors associated with repeated revisions. There were no MESH words containing "rerevision", "multiply revisions" or "repeated revisions".

Articles found: 4350 results.

Based on the title, this number of abstracts were reviewed: 97

Of the abstracts, so many articles were reviewed and read: 65

Number of articles used in the protocol: 47.

Material and methods

Design

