In WP-A1 we want to calculate:

- 1) Annual incidence of revision arthroplasties.

Incidence is calculated as the number of n-grade revisions performed in Denmark during a given year as a proportion of the current year's population. This is done for each level of revision.

The incidence rate is also calculated:

$$IR = \frac{\text{Number of } n\text{-grade revisions}}{\text{Number of person-years in observation period}}$$

- 2) The continuous prevalence of revision knees.

Prevalence is calculated as the number of patients living with n-grade revision knee as a proportion of the current year's population. This is done for each level of revision.

- 3) The relationship between the annual incidence of n-grade revisions with the incidence of primary procedures in the preceding years.

$$\text{rate ratio} = \frac{\text{IR for } n - \text{ grade revision}}{\text{IR for primary procedures the previous year}}$$

WPA2

The analyzes will be based on the population defined in WP-A1. We will estimate the cumulative incidence (risk) for the different levels of revision and examine whether factors such as patient demographics, implant type and other operative technical conditions influence the cumulative incidence.

$$\begin{aligned} & \text{risk for } n - \text{ grade revision} \\ & = \frac{\text{number of } n - \text{ grade revisions in the observation period}}{\text{numbers with } n - 1 \text{ revisions}} \end{aligned}$$

To investigate whether patient demographics, implant type, indication for revision and other operative technical conditions have an effect on the subsequent incidence of revision, we will use regression analysis. It will be relevant to investigate possible confounding of the variables.

In addition, we will create "cumulative incidence plots" for each level of revision to illustrate prosthesis survival.

WPA3

The lifetime risk will be determined as a summation of the expected remaining life based on the CRR for the individual events (primary procedure and n-grade revision). As in WPA2, we will examine whether patient demographics, implant type and other operative technical conditions have an effect on the risk of revision. In addition, the lifetime risk of arthrodesis or amputation as an event will also be calculated. Thus, data from WP-A2 becomes the starting point for the calculations.

Applicant's duties

The applicant's duties consist of:

The overall responsibility for the execution of the project.

Obtaining necessary data approvals.

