#### 4. PROTOCOL DEVIATIONS WITH BEARING ON THIS STATISTICAL ANALYSIS PLAN

---

The following details in this SAP represent deviations from the protocol.

Header in the protocol	Change	Reason
(currently no deviations)		

[figure not shown]

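### The WP-A1 rate ratio divides n-grade revisions by one previous year of primaries, so it cannot answer its own question about the preceding years

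*Protocol*

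**What the plan says.** Research question 3 under WP-A1 (Protocol, Purpose) reads: "What is the relationship between the annual incidence of revisions of n-grade with the incidence of primary procedures in the preceding years". Item 3 under WPA1 in the Statistics section repeats the aim: "The relationship between the annual incidence of n-grade revisions with the incidence of primary procedures in the preceding years". Both speak of several years.

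The formula beneath item 3 divides the incidence rate (IR) of n-grade revision by "IR for primary procedures the previous year". That is one calendar year, and it does not change with n. No longer lag, distributed lag or linkage to the year of the primary is specified for this question.

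The purpose paragraph of WP-A1 also announces a model that predicts future incidence and prevalence "based on demographic data as well as historical information of primary knee arthroplasty".

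On timing, the Re-revision section of the Background reports from one study that "re-revisions were performed 4 years since the last revision, while first revisions were performed after 8 years since primary knee arthroplasty". The protocol describes that study as a "smaller population of 300 patients in a prospective, single-centre study". Under Size of the problem, about 13% of primaries are said to have a first revision within 20 years. Multiply revised means "at least three revisions of their knee replacement".

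The SAP defines annual prevalence and incidence only. None of its tables or figures contains the ratio, and its section 4 on protocol deviations states "currently no deviations".

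**The concern.** The formula and the question differ. A revision in year t that follows a primary in year t-1 comes less than two years after that primary. For a third revision, all three revisions would have to fall within that time. A denominator limited to year t-1 is therefore mostly the wrong cohort, and most clearly so for the multiply revised knees that the project is about.

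The ratio would then respond to two things at once: revision risk in knees implanted over many years, and how many primaries happened to be done last year. If primary volume rises, the ratio falls without any improvement in revision risk. If volume drops, it rises without any deterioration. A reader who took a trend in this ratio as a trend in revision burden per primary, or carried it into planning of future demand, could be misled.

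**Working it through.** The documents give no value for the ratio, so there is no figure to reproduce. The check has three parts.

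**1. Typical lag by grade.** Inputs: 8 years to first revision and 4 years between revisions (Protocol, Re-revision). Assumption: the gaps add up, and the 4-year gap holds at every grade.

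Lag(n) = 8 + 4 × (n - 1).

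- n = 1: 8 years
- n = 2: 12 years
- n = 3: 16 years
- n = 4: 20 years
- n = 5: 24 years

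Only the 8 and the 4 are stated; the rest is derived. The formula uses 1 year for all grades.

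**2. How far the denominator could be off.** Inputs: more than 150,000 primaries in 20 years and about 10,500 in 2020 (Protocol, Background), a mean of 150,000 / 20 = 7,500 a year. No other annual count is given, so the path over 2001-2020 is assumed, with 150,000 taken as the total. The factor is primaries in 2019 divided by primaries in 2020 - L.

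*Linear growth.* The start is 2 × 7,500 - 10,500 = 4,500, and the yearly step is 6,000 / 19 = 315.8. Primaries are 10,184 in 2019, 7,974 in 2012, 6,711 in 2008 and 5,447 in 2004.

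*Constant percentage growth.* The same total and end value give 3.87% a year, and the factor is 1.0387^(L - 1).

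*Plateau.* 10,500 a year in 2009-2020 makes 126,000. The remaining 24,000 over 2001-2008, if spread evenly, is 3,000 a year.

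| Assumed path | L = 8 | L = 12 | L = 16 |
|---|---|---|---|
| Linear | 1.28 | 1.52 | 1.87 |
| Constant percentage | 1.30 | 1.52 | 1.77 |
| Plateau from 2009 | 1.00 | 3.50 | 3.50 |
| Flat volume | 1.00 | 1.00 | 1.00 |

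The plateau's 3.50 is 10,500 / 3,000 and is an extreme case. Flat volume sits poorly with a 2020 count of 10,500 against a mean of about 7,500.

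A fixed lag is not needed for the effect. If revisions are spread evenly over lags of 1 to 19 years, the mean of the contributing years is (150,000 - 10,500) / 19 = 7,342. The factor is then 10,184 / 7,342 = 1.39 (linear) or 10,109 / 7,342 = 1.38 (constant percentage). If early lags dominate (assumed weights exp(-k/4) for k = 1 to 19), it is 1.12 to 1.13 under the two growth paths.

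These are ratios of counts. The formula uses IRs, so population growth between the two years would reduce the factors somewhat. The documents give no population figures.

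**3. Index years available.** With data for 1998-2021, a denominator at lag L exists for 2021 - (1998 + L) + 1 = 24 - L index years: 23 at a one-year lag, 16 at L = 8, 12 at L = 12, 8 at L = 16, 4 at L = 20 and none at L = 24.

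**The case against.** Several points against a stronger reading stand.

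- A reader might take 8 to 16 years as documented. It is not. The 8 and 4 come from a single centre, with no statement of whether they are means or medians, and the 16 is 8 + 4 + 4. The Background also reports from a national register study that 20% had a third revision after 5 years and 20% of those a fourth within 3 years, with higher risk when the time between revisions is shorter. Gaps may therefore shorten with grade, and the 16 years is the least certain figure.
- A reader might infer that almost no revisions come from the previous year's primaries. That needs a lag distribution, which the documents do not give. Some first revisions are early.
- A reader might conclude that the ratio is biased downward by 1.28 to 1.87. The direction and size follow from assumed growth. The plateau fits the same totals and gives no effect at 8 years.
- A reader might say that the forecast fails. The protocol does not state that this ratio feeds the prediction model, and WP-A2 estimates revision risk by grade separately.
- SAP section 4 lists no deviation, but that does not show that the ratio will be reported. The SAP may simply have left it out.

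None of this removes the mismatch between a question about several years and a formula that uses one.

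**Conclusion.** The formula in WPA1 item 3 does not answer research question 3. That conclusion needs only the protocol's own wording. It is reinforced by the cited intervals and by first revisions being spread over 20 years, which place most n-grade revisions, especially third and later, after primaries from earlier years.

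The ratio therefore mixes recent primary volume with revision risk. How much, and in which direction, cannot be settled from the documents. Under steady growth the illustrative factors are about 1.3, 1.5 and 1.8-1.9 at lags of 8, 12 and 16 years. They range down to 1.0 with flat volume, and to 1.0 at lag 8 with larger values at longer lags under a plateau. They should not be quoted as a known bias.

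The SAP neither repairs the formula nor declares the analysis dropped. The point should be corrected before analysis. It does not touch the annual incidence and prevalence that form the SAP's primary outcome.

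**What to change.** Replace the item 3 formula with a relation over all preceding primary years. Table G (Protocol, Organization of data) already dates revisions, deaths and emigration for each knee. Two forms would serve:

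1. **By primary cohort.** Report n-grade revisions in year t by year of the primary, each as a proportion of that primary cohort.
2. **Distributed lag.** Expected n-grade revisions in year t = sum over k of (primaries in year t - k) × (probability that the n-th revision occurs k years after the primary), with death as a competing event. If observed/expected is reported, use one lag distribution pooled over calendar years and say that it comes from the same cohort. The comparison is then partly circular and shows departures from the average pattern only.

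Do not substitute one fixed median lag. It repeats the single-year error, and a median observed within a 24-year window is biased short. State the left truncation at 1998, and leave out early index years and high grades with too little history.

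If item 3 is not to be analysed, list this in SAP section 4 with the reason, and mark research question 3 accordingly.

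The cost is revised wording and modest extra analysis on data already planned, with fewer usable index years at higher grades. Declaring the item dropped costs one table row.
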